#### 5.4.3 Axitinib induced hypertension management

Patients will be asked to keep a home log of daily blood pressure and will be instructed NOT to take axitinib if blood pressure is  $> 150 \times 90$  mmHg with two consecutive readings and additional antihypertensives will be added to control BP to target and resume Axitinib

Management of hypertension is as follow:

**Grade 1:** No dose modification.

**Grade 2:** Withhold axitinib. Start and/or optimize anti-hypertensive therapy per institutional policy. Patient may resume axitinib after blood pressure is  $< 150 \times 90$  mmHg.

**Grade 3:** Requires more than one antihypertensive drug or more intensive therapy than previously. If not controlled to  $150 \times 90$  mmHg with medication, dose reduction required.

**Grade 4:** Discontinue axitinib when on 4 or  $>$  antihypertensive medications and blood pressure remains  $> 150/90$  or symptoms related to hypertensive urgency.

## Proprietary of MD Anderson Cancer Center

### 5.5 Investigational product supplies

Avelumab and axitinib will be supplied for the study by Pfizer Global Clinical Supply, Worldwide Research and Development. Drug supplies will be shipped to the study site with a Drug Shipment and Proof of Receipt form. This form will be completed, filed, and the shipment confirmed as directed on the bottom of the Drug Shipment and Proof of Receipt form. The Investigator shall take responsibility for and shall take all steps to maintain appropriate records and ensure appropriate supply, storage, handling, distribution, and usage of investigational products in accordance with the protocol and any applicable laws and regulations.

### 5.6 Investigational product accountability

The investigative site must maintain adequate records documenting the receipt, use, loss, or other disposition of all investigational product supplies. Patients receiving axitinib will be required to return all unused study treatment at the beginning of each cycle. Pill count will be performed by research staff. Drug accountability will be maintained by our pharmacy team. Returned drug will be disposed of per MD Anderson institutional policy.

The study drug Supporter or designee will provide guidance on the destruction of unused investigational products (e.g., at the site). If destruction is authorized to take place at the study site, the investigator must ensure that the materials are destroyed in compliance with applicable environmental regulations, institutional policy, and any special instructions provided by Pfizer, and all destruction must be adequately documented.

### 5.7 Investigational product storage

The Investigator, or an approved representative, e.g., pharmacist, will ensure that all investigational products are stored in a secured area with controlled access under required storage conditions and in accordance with applicable regulatory requirements.

Site systems must be capable of measuring and documenting (for example, via a log), at a minimum, daily minimum and maximum temperatures for all site storage locations (as applicable, including frozen, refrigerated and/or room temperature products). This should be captured from the time of investigational product receipt throughout the study. Even for continuous monitoring systems, a log or site procedure that ensures active daily evaluation for excursions should be documented. The operation of the temperature monitoring device and storage unit (for example, refrigerator), as applicable, should be regularly inspected to ensure it is maintained in working order.

Any excursions from the product label storage conditions should be reported upon discovery.

The site should actively pursue options for returning the product to the storage conditions as described in the labeling, as soon as possible. Deviations from the storage requirements, including any actions taken, must be documented and reported to the study Supporter.

Once an excursion is identified, the investigational product must be quarantined and not used until the study Supporter provides documentation of permission to use the investigational product. It will not be considered a protocol deviation if the study Supporter approves the use of the investigational product after the temperature excursion. Use of the investigational product prior to study Support approval will be considered a protocol deviation.

Avelumab must be stored at 2 to 8 °C or 36 to 46 °F DO NOT FREEZE

Avelumab must be allowed to reach room temperature for a minimum of 30 minutes prior to use in dose preparation. The immediate administration of the prepared solution for dosing kept at room temperature is preferred. In case the aseptically prepared dosing solution cannot be administered immediately after preparation, the acceptable holding time is: not more than 24 hours under refrigerated conditions (2-8°C, 36-46°F) with no more than 8 of those hours at room temperature (15-25°C, 59-77°F), including infusion time.

If stored under refrigerated conditions, allow each bag to equilibrate to room temperature (15-25°C, 59-77°F), preferably for one hour before administration

## 5.8 Preparation and administration of Avelumab

- Avelumab infusion solutions must be prepared in 0.9% Sodium Chloride (Normal Saline) and the final concentration of avelumab in the infusion solutions must be between 0.016 mg/mL to 8 mg/mL.
- Total volume of final prepared solution must be 250 mL.
- Parenteral investigational drug products must be inspected visually for particulate matter and discoloration (i.e. change in color) prior to administration, whenever the solution and container permit. If particulates or discoloration are observed, do not use the vial(s) and notify Pfizer.
- Do not shake or freeze the vial(s).
- The expiry time of final IP is 24 hours from the time the vials were removed from the refrigerator and allowed to reach room temperature: 24 hours under refrigerated conditions (2-80 C, 36-460F) with no more than 8 of those hours at room temperature (15-250C, 59-770F), including infusion time. Dose preparation must be performed using sterile handling techniques in compliance with local, state, and national laws/regulations.
- Avelumab MUST be administered with a low protein binding 0.2 micron PES filter.
- Each vial is for single-use only. Each vial is for use in a single patient, for a single dose.

## 5.9 Treatment duration

Subjects will continue treatment until confirmed disease progression, unacceptable toxicity, refusal to participate further, or loss to follow-up. Patients with evidence of disease progression per RECIST 1.1 (see appendix 1), who were still experiencing clinical benefit could be considered for continuation of treatment as per the investigator's clinical judgment and after discussion between the investigator and study Supporter.

If patients develop unacceptable toxicity attributed to one of the study treatments leading to discontinuation, they could continue receiving the other study treatment.

# Proprietary of MD Anderson Cancer Center

## 6. Study Calendar and Procedures

Table 6

Required Procedures	Screening (baseline)	During Treatment	End of Treatment/ Safety Follow-up Visit 	Long Term Follow-Up 
Timing	Within 28 days prior to treatment initiation unless otherwise specified	Every 4 weeks, $\pm$ 7 days, unless otherwise specified	30 days $\pm$ 7 days after last dose of study treatment	
Consent	X 			
Treatment History	X			
Medical History	X			
Demographics	X			
Physical Exam	X	X	X	
Vital Signs	X	X	X	
Height	X			
Weight	X	X	X	
ECOG PS	X			
Axitinib dosing		X Twice daily		
Avelumab dosing		X every 2 weeks		
Symptoms & Toxicities	X	X On an ongoing basis throughout study	X	
Concomitant Medications	X	X On an ongoing basis throughout study	X	
Hematology Profile	X	X every 2 weeks prior to avelumab dosing	X	
Chemistry Profile  , phosphorous 	X	X every 2 weeks prior to avelumab dosing	X	
GGT	X			
aPTT and INR	X			

# Proprietary of MD Anderson Cancer Center

EKG	X			
Echocardiogram	X	X 		
Urine analysis for proteinuria	X	X 		
Pregnancy Test (serum or urine) for all women of child bearing potential 	X	X 		
Radiology & Tumor Measurements 	X	X Every 8 weeks, ± 7 days		X
Biopsy	X If archived tissue not available			
Blood-based biomarkers	X 	X 		
Study Drug Compliance		X At each clinic visit		
Subsequent Anticancer Therapy				X
Survival Status				X

1 Written informed consent will be given by each patient prior to undergoing protocol specific evaluation and prior to receiving treatment

2 Chemistry profile includes: BUN, creatinine, sodium, potassium, carbon dioxide, magnesium, total bilirubin, alkaline phosphatase, aspartate aminotransferase, alanine aminotransferase, total protein, and serum phosphorus

3 Serum or urine pregnancy test will be obtained at baseline within 7 days prior to treatment and monthly during treatment in all women of child bearing age and again if clinically indicated

4 CT scan, PET CT scan of the chest/abdomen/pelvis and/or MRI of base of skull/orbit/face as clinically indicated. CT scan or MRI of the brain if clinically indicated

5 Long term follow-up will occur every 6 months by medical/clinical data review or phone contact

6 For patients who discontinue treatment due to reasons other than disease progression, tumor assessment will continue as per during the treatment schedule (i.e. radiology & tumor measurements every 8 weeks +/- 7 days).

7 Extended safety follow up: given the potential risk of immune-related toxicity, safety follow up will be performed up to 90 days after the last dose of avelumab administration. The extended follow up beyond 30 days after last avelumab administration may be performed either via a site visit or via a telephone call with subsequent site visit requested in case any concerns noted during the telephone call

8 Blood will be collected on at baseline (pre-treatment), day 7 (optional), day 15, prior to C3D1, and at progression (optional). Three categories of specimen will be collected: EDTA Vacutainer (checkpoint markers/CAFs): 10 mL = 1 x 10 mL; Streck CF-DNA BCT (ctDNA): 10 mL = 1 x 10 mL; and Sodium Heparin (immunoprofiling): 60 mL = 6 x 10 mL. All blood will be collected and processed by the Thoracic Research Team ([name] laboratory) according the institutional and laboratory standard operating procedures (SOPs).

9 While on treatment as clinically indicated

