#### 1.3.1 Axitinib clinical experience

The table below summarizes the most common treatment-emergent all-causality AEs reported in  $\geq 10\%$  cancer subjects who received single agent axitinib. The majority of subjects (98%; 1445/1474) reported at least one AE (all grade) and 73.7% (1086/1474) reported at least one grade  $\geq 3$  AE.

For single-agent axitinib, the most common treatment emergent all causality AEs reported from 1474 cancer subjects were: diarrhea 55.0%, hypertension 51.0%, fatigue 47.1% , decreased appetite 40.0% , nausea 32.6% ,weight decreased 32.2% , dysphonia 31.1% , palmar-plantar erythrodysaesthesia syndrome 29.4% , hypothyroidism and vomiting 22.6% , constipation 20.3% , proteinuria 20.1% . The most frequent Grade  $\geq 3$  events were: hypertension 20.7%, fatigue 10.2%, and diarrhea 10.1%.

Table. All-causality adverse events reported in  $\geq 10\%$  patients who received single agent axitinib

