therapy directly per protocol. Patients in the dose-finding cohort received a median of 32·5 avelumab infusions (IQR 31·0–37·0) during a median follow-up of 69·7 weeks (IQR 66·1–74·1). The median duration of treatment was 66·6 weeks (IQR 66·0–74·1) with axitinib and 66·0 weeks (IQR 65·6–74·0) with avelumab. Among the six patients in the dose-finding cohort, four (67%) had a grade 3 or 4 treatment-related adverse event (grade 3 hypertension, palmar-plantar erythrodysaesthesia, proteinuria, and mucosal inflammation and grade 4 increase in lipase concentration). One patient had a dose-limiting toxicity (grade 3 proteinuria) that led to axitinib dose reduction and resolved without sequelae; this patient continued treatment with avelumab at 10 mg/kg and 3 mg axitinib twice daily. One patient discontinued axitinib due to grade 3 palmar-plantar erythrodysaesthesia syndrome. This patient continued treatment with avelumab monotherapy until disease progression. At the end of the dose-finding phase, the maximum tolerated dose established for the combination was avelumab 10 mg/kg every 2 weeks and axitinib 5 mg twice daily. There was no differences in antitumor activity or safety between patients in either phase who received lead-in treatment with axitinib and those who did not. At the cutoff of April 13, 2017, the median follow-up for all 55 patients was 52·1 weeks (IQR 37·4–56·1). 54 (98%) patients received avelumab and axitinib, and one patient received only axitinib because of an adverse event (grade 3 increase in blood creatine phosphokinase concentration) that arose before avelumab was started. At the time of cutoff, combination treatment was ongoing in 29 (53%) of 55 patients, two (4%) were receiving treatment with axitinib alone, and one (2%) was receiving avelumab alone. Patients received avelumab for a median of 37·0 weeks (IQR 14·0–50·0) and axitinib for a median of 36·0 weeks (IQR 18·1–50·1). Reasons for treatment discontinuation were progressive disease (n=11 for avelumab and n=14 for axitinib), adverse events (n=7 for avelumab and n=4 for axitinib), withdrawal of consent (n=3 for both treatments), death (n=2 for both treatments), and physician's decision (n=1 for both treatments). All 55 patients experienced at least one adverse event during the trial, and 53 (96%) had one or more adverse events that were judged by the investigator to be related to avelumab or axitinib. The most frequent treatment-related adverse events (occurring in  $\geq 10\%$  of patients) included diarrhea, hypertension, dysphonia, fatigue, palmar-plantar erythrodysaesthesia syndrome, increased alanine aminotransferase concentration, rash, increased aspartate aminotransferase concentration, hypothyroidism, increased amylase concentration, decreased appetite, mucosal inflammation, infusion-related reactions, increased lipase concentration, and nausea. 32 (58%) of 55 patients had grade 3 or worse treatment-related adverse events and one died from treatment-related autoimmune myocarditis (confirmed by widespread myocarditis on post-mortem histopathology; viral cause was excluded). 16 (29%) of 55 patients reported infusion-related reactions, most of which were grade 1 or 2; one (2%) patient had a grade 3 infusion-related reaction and discontinued avelumab, and one (2%) additional patient had chills unrelated to treatment. 16 (29%) of 55 patients had infusion-related reactions with the first infusion, and one (2%) had three grade 2 infusion-related reactions at cycles eight, nine, and ten, but continued treatment beyond cycle ten until disease progression. 23 (42%) of 55 patients had immune-related adverse events; see appendix for adjudication criteria. The most frequent was hypothyroidism in 13 (24%) patients, and five (9%) had grade 3 or worse immune related events, which led to avelumab dose interruption in one patient (due to rash) and discontinuation of Avelumab in the other four patients. 20 (36%) of 55 patients had serious adverse events, which were judged to be treatment related in 12 (22%). Serious adverse events occurring in more than one patient were increased alanine aminotransferase concentration (n=2, deemed to be treatment related), infusion-related reactions

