
(n=2 related to avelumab), and presyncope, spinal cord compression, and hypoxia (all n=2, not related to study treatment). Ten (18%) of 55 patients discontinued one or both study drugs due to adverse events. Seven (13%) of 55 discontinued avelumab, with increased alanine aminotransferase concentration being the only adverse event leading to discontinuation in more than one patient (n=3 [6%]). Four (7%) of 55 patients discontinued axitinib (no events occurred in more than one patient). Six (11%) of 55 patients died before data cutoff: five (9%) due to disease progression (four after the end of treatment) and one (2%) due to treatment-related autoimmune myocarditis. 32 (58%) of 55 patients had avelumab dose delays, with duration of 7 days or longer in 25 (46%) of 55 patients. Four (7%) of 55 patients received less than 90% of the planned avelumab dose in one infusion because of adverse events: three due to infusion-related reactions (one of whom discontinued treatment) and one due to an electrocardiogram abnormality unrelated to study treatment. Axitinib was decreased at least once in 31 (56%) of 55 patients and increased at least once in ten (18%) of 55 patients. Axitinib dose reductions were due to adverse events in 28 (51%) of 55 patients, among whom the most common (in >5% of patients) were palmar-plantar erythrodysaesthesia syndrome (n=6), fatigue (n=5), hypertension (n=4), and proteinuria (n=3).

Table. Treatment-related adverse events occurring in  $\geq 10\%$  of patients

Table 2

	All grades	Grade 3	Grade 4	Grade 5
All events	53 (96%)	26 (47%)	5 (9%)	1 (2%)
Diarrhoea	32 (58%)	2 (4%)	0	0
Dysphonia	26 (47%)	0	0	0
Hypertension	26 (47%)	16 (29%)	0	0
Fatigue	25 (46%)	2 (4%)	0	0
PPE syndrome	17 (31%)	4 (7%)	0	0
ALT increased	16 (29%)	4 (7%)	0	0
Rash	16 (29%)	1 (2%)	0	0
AST increased	14 (26%)	1 (2%)	0	0
Hypothyroidism	14 (26%)	0	0	0
Amylase increased	13 (24%)	3 (6%)	1 (2%)	0
Decreased appetite	13 (24%)	1 (2%)	0	0
Mucosal inflammation	13 (24%)	1 (2%)	0	0
Infusion-related reaction*	11 (20%)	1 (2%)	0	0
Lipase increased	11 (20%)	1 (2%)	3 (6%)	0
Nausea	11 (20%)	1 (2%)	0	0
Arthralgia	9 (16%)	1 (2%)	0	0
Weight decreased	9 (16%)	1 (2%)	0	0
Pruritus	8 (15%)	0	0	0
Dysgeusia	7 (13%)	0	0	0
Stomatitis	7 (13%)	0	0	0
Dyspnoea	6 (11%)	0	0	0
Myalgia	6 (11%)	0	0	0
Proteinuria	6 (11%)	2 (4%)	0	0
Vomiting	6 (11%)	0	0	0
Hypophosphataemia	5 (9%)	2 (4%)	0	0
Blood triglycerides increased	4 (7%)	1 (2%)	0	0
Dehydration	3 (6%)	1 (2%)	0	0
Pain in extremity	3 (6%)	1 (2%)	0	0

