## 5.3 Safety assessment

For details see section 6(study calendar and procedures)

1. Blood chemistry and hematology assessments: must be performed at screening, prior to each avelumab dose, at end of treatment visit and at 30 days post-treatment safety follow-up.
2. Urine pregnancy test for women of childbearing potential must be performed at baseline and at least every month during treatment.
3. Free T4 and TSH must be performed at baseline and at least every 8 weeks during treatment and at end of treatment or 30 days post-treatment safety follow-up (if not performed in the previous 8 weeks).
4. Extended safety follow up: give the potential risk of immune-related toxicity, safety follow up will be performed up to 90 days after the last dose of avelumab administration. The extended follow up beyond 30 days after last avelumab administration may be performed either via a site visit or via a telephone call with subsequent site visit requested in case any concerns noted during the telephone call.

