#### 5.4.2 Axitinib dose modification

If a patient experiences a CTCAE grade 3 or higher and/or unacceptable toxicity (any grade), where the clinician considers the event of concern to be specifically associated with axitinib (and not attributable to the disease, disease-related processes for which patient is being treated, or to avelumab), dosing will be interrupted and supportive therapy administered as required in accordance with local practice/guidelines. If the toxicity resolves or reverts to  $\leq$ CTCAE grade 2 within 3 weeks of onset, treatment with axitinib may be restarted at the same dose or a lower dose using the rules below for dose modifications. There will be no individual modifications to dosing schedule in response to toxicity, only potential dose reduction or dose interruption. If the toxicity does not resolve to  $\leq$ CTCAE grade 2 after 3 weeks, then the patient should be withdrawn from the study and observed until resolution of the toxicity.

**Table 5.** Axitinib Dose interventions

Intervention	Axitinib dose
Starting dose	5 mg orally BID
Level -1	3 mg orally BID
Level -2	2 mg orally BID

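### On-treatment urinalysis for proteinuria has no fixed interval, so asymptomatic grade 3 cases could be missed on a combination whose dose-finding phase reported one such dose-limiting toxicity

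*Combined protocol and SAP*

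**What the plan says.** Table 6 has a row labelled "Urine analysis for proteinuria". It is marked at screening and during treatment; the on-treatment mark refers to footnote 9, "While on treatment as clinically indicated". The end-of-treatment column is empty.

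Section 5.3 lists safety tests with fixed timing: chemistry and hematology before each avelumab dose, thyroid tests at least every 8 weeks, and for pregnancy "Urine pregnancy test for women of childbearing potential must be performed at baseline and at least every month during treatment". Urinalysis is not in that list. The laboratory paragraph of Section 6.1 refers back to the calendar and allows more frequent tests if indicated.

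At entry the plan is stricter. Exclusion criterion 15 sets limits on urine protein and requires a 24-hour collection when the baseline urinalysis shows 150 mg/dL or more.

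Section 1.4 reports on six dose-finding patients treated with this combination: "One patient had a dose-limiting toxicity (grade 3 proteinuria) that led to axitinib dose reduction and resolved without sequelae". Among the reasons for axitinib reduction in the full 55 patients it lists "fatigue (n=5), hypertension (n=4), and proteinuria (n=3").

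Section 5.4.2 says that for grade 3 or higher toxicity attributed to axitinib, "dosing will be interrupted and supportive therapy administered as required in accordance with local practice/guidelines". If the toxicity has not come down to grade 2 or lower after 3 weeks, the patient is withdrawn.

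**The concern.** Proteinuria is found by testing urine and can be present without symptoms. The plan's own background names it as the reported dose-limiting toxicity of this combination in the dose-finding phase, and the plan controls it at baseline. After baseline, whether and when urine is tested is left to the clinician.

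Two things are at stake.

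- **Patient safety.** The Section 5.4.2 interruption can act only on toxicity that has been detected.
- **The safety results.** Safety is a secondary objective, and Section 9.1 analyzes it in all patients who received any treatment. A patient whose urine was never tested on treatment is counted as having no proteinuria, so the reported rate may be too low. With 30 patients, each missed case lowers it by 1/30 = 3.3 percentage points.

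**Working it through.** **1. Is an interval set anywhere?**

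- The on-treatment column of Table 6 has a 4-weekly default, but that default gives way where something else is specified. Footnote 9 specifies something else.
- The pregnancy test also carries footnote 9, but footnote 3 and Section 5.3 separately make it monthly. Urinalysis has no such second source.
- Section 6.1 adds no interval.

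So none is set.

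**2. What else is scheduled that could prompt a urine test?** Chemistry every 2 weeks (including creatinine, BUN and total protein); physical exam, vital signs and weight every 4 weeks; ongoing symptom and toxicity review; and, in Section 5.4.3, "Patients will be asked to keep a home log of daily blood pressure". None of these measures urine protein. The gap is therefore limited to proteinuria that produces none of these prompts.

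**3. How often might proteinuria occur?** Inputs are the combination study (Section 1.4 and Table 2) and single-agent axitinib (Table 1). Intervals are exact (Clopper-Pearson) 95%. The last column is 30 times the rate.

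| Event | Rate | 95% CI | Expected in 30 |
|---|---|---|---|
| Related proteinuria, combination | 6/55 = 10.9% | 4.1% to 22.2% | 3.3 |
| Grade 3, combination | 2/55 = 3.6% | 0.4% to 12.5% | 1.1 |
| Axitinib reduction for proteinuria, combination | 3/55 = 5.5% | 1.1% to 15.1% | 1.6 |
| All-causality, axitinib alone | 296/1474 = 20.1% | 18.1% to 22.2% | 6.0 |
| Grade 3 or worse, axitinib alone | 59/1474 = 4.0% | 3.1% to 5.1% | 1.2 |

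The 3/55 agrees with the document's own description of causes seen in more than 5% of patients. The dose-limiting case may be one of those three reductions, so the two counts should not be added.

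For grade 3 in 30 patients:

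- Expected number: 30 × 2/55 = 1.09. At the CI limits (0.443% and 12.53%): 0.13 and 3.8.
- Chance of at least one: 1 − (53/55)^30 = 0.67. At the CI limits: 1 − (1 − 0.00443)^30 = 0.12 and 1 − (1 − 0.1253)^30 = 0.98.

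These figures describe proteinuria occurring, not proteinuria missed.

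**4. Does the cycle 1 stopping rule suffer?** With the Beta(0.3, 0.7) prior, stopping when the posterior probability of a toxicity rate above 0.30 exceeds 0.7, and looks from patient 7 to 29, an exact calculation reproduces every boundary in Table 8 and every value in Table 9 (0.032, 0.225, 0.584, 0.876, 0.982). The counted toxicity rate is then lowered by the missed part.

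| Cycle 1 grade 3 proteinuria missed | True 30% | True 40% | True 50% |
|---|---|---|---|
| None | 0.584 | 0.876 | 0.982 |
| 2/55 (extreme bound for that rate) | 0.447 | 0.792 | 0.961 |

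The extreme bound needs every grade 3 case to start in cycle 1, meet the Section 9.2 toxicity definition, occur in a patient with no other counted toxicity, and be missed. That definition counts a laboratory-only finding mainly if it needs intervention, leads to admission or prevents 75% of axitinib doses. If half of the 2/55 fell in cycle 1 (assumption: 1/55 missed), 0.876 would fall to 0.837. The documents do not give onset times.

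**The case against.** **Discretion is not absence.** Footnote 9 leaves urinalysis available at any time, and an investigator may test routinely. Chemistry, examination, toxicity review and the blood pressure log narrow the truly silent remainder. This stands. A reader might infer that silent grade 3 proteinuria would go undetected under the plan; the documents support only that it could, and they give no basis for estimating the share missed.

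**The rates are borrowed and imprecise.** They come from renal cell carcinoma, the grade 3 figure rests on two patients, and patients with significant baseline proteinuria are excluded here. The background gives no proteinuria rate from the earlier axitinib study in this tumor. This also stands, which is why the 67% must be read with its 12% to 98% range. The much larger single-agent series gives a similar expected count (1.2 grade 3 or worse in 30).

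**The known dose-limiting case resolved without lasting harm.** True, but it resolved after it was found and axitinib was reduced, which is an argument for looking.

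**More testing may cost treatment.** Routine testing could produce more interruptions, and Section 5.4.2 withdraws patients whose toxicity has not come down after 3 weeks, while Section 5.4 asks for effort to continue axitinib. This is a real cost and is counted below.

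**The EKG row.** Section 5.4 has a rule for QTc above 500 msec and cardiology review at 470 to 499 msec, yet Table 6 marks the EKG at screening only. A reader might infer a second monitoring gap of equal weight. The documents do not support that. Table 6 as read is visibly incomplete: the thyroid tests that Section 5.3 requires have no row, and footnote 6 is attached to no cell. No QTc event rate is given, EKGs for cause remain possible, and Section 5.4 itself expects on-treatment EKGs. It is a query and no more.

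**Conclusion.** The point holds as a safety-monitoring gap that is cheap to close. On-treatment urine testing rests on clinical discretion alone, for a toxicity that the background identifies as dose-limiting for this combination. Asymptomatic grade 3 proteinuria could be missed, and the reported rate could be too low.

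The size rests on the renal cell rates carrying over: about one grade 3 case in 30 patients, plausibly anywhere from none to four. How many would be missed is unknown.

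A reader might infer that toxicity monitoring as a whole is compromised. That does not follow. The loss in stopping probability at a true 40% rate is at most 0.876 − 0.792 = 0.084 for the 2/55 rate, under conditions that are unlikely to hold together. The response-rate analysis, the sample size and the two-stage design's error rates are unaffected.

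**What to change.** In the urinalysis row of Table 6, replace footnote 9 with testing at the existing 4-weekly visits, the first by the end of cycle 1, and more often if clinically indicated. Add a 24-hour collection when the result is 150 mg/dL or above, unless the study clinicians set another level; that figure is the eligibility threshold of exclusion 15 and was not written for on-treatment use. Leave the dose rules as they are.

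Cost: a calendar amendment and about 36/4 = 9 urinalyses per patient if axitinib lasts the 36-week median of the renal cell study (assumption), or 9 × 30 = 270 in all. No new visits or invasive procedures are needed. The downsides are occasional 24-hour collections, incidental findings, and possibly more axitinib interruptions or withdrawals under Section 5.4.2.

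As a query only, ask the study team to confirm whether the EKG row should have an on-treatment entry, since the Section 5.4 QTc rule has no scheduled EKG to feed it.
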